7.2. Data management

Pockit diagnostics is responsible for the data management of this study including quality checking of the data.

All clinical data collected for the purpose of this study are recorded in a Case Report Form (CRF). The CRF will function as the source data if data is not detailed in patient charts or if described in this protocol.

An integrated database for this study will include all clinical data (provided by hospital site within the CRF) and biomarker data (detailed in section 7.1). The clinical database will be locked once all data entry, validation and reconciliation of queries has been completed and a final curation of the collected biomarker data has been completed. The data will subsequently be analysed according to the data analysis plan detailed in section 7.4.

Brain images will only be used to establish final patient diagnosis and will not be part of the CRF. Brain images will not be shared with anyone outside hospital site.

Pockit diagnostic personnel involved in running subject samples will be blinded to any clinical data pertaining to the nature of these samples.

7.3. Data storage

All electronic data will be stored on a secure server with restricted access to authorised Pockit diagnostics personnel only. All information will be sent to and -if applicable -from this server through a secure encrypted connection.

Blood samples may be partially or fully utilised as part of the analysis process. Blood samples will be stored at Pockit diagnostic premises (Cambridge, UK). All samples will be handled in accordance with the Human Tissue Act 2004, and Material Transfer Agreements will be put in place as required by Pockit diagnostics and hospital site. Upon collection, samples will be stored at hospital site, until shipment to Pockit diagnostics. Samples will be analysed all at the same time, and only after all samples have been received by Pockit diagnostics. Samples could be analysed for a period up to 10 years after completion of this study, after which they will be destroyed following standard procedures. During this period data might be used for other studies conducted by Pockit diagnostics.

Study records and documents at the clinical site, including signed Informed Consent Forms (ICFs), pertaining to the conduct of this study must be retained by the hospital for at least 2 years after study completion unless local regulations or institutional policies require a longer retention period.

No records may be destroyed during the retention period without the written approval of Pockit diagnostics. No records or data may be transferred to another location or party without written notification to Pockit diagnostics.

7.4. Data analysis plan

Clinical and biomarker data will be curated after clinical and technical monitoring to assure maximum validity of the data utilised to construct the algorithm. Any subject matching

criteria as defined in section "6.3 – Withdrawal criteria" will not be incorporated into the primary analysis. This data is quarantined for a separate sub-group analysis where relevant.

Data exploration

Data will be explored by generating box plots of blood biomarker concentrations (plasma or whole blood) and clinical data, according to stroke subtypes. Concentrations of blood biomarkers and clinical data (where applicable) may undergo pre-processing and/or transformations to ensure statistical assumptions are met prior to analysis. Akaike information criterion (AIC) will be used to assess the need of transformations.

Whole blood biomarker concentrations

Plasma concentration of individual biomarkers will be adjusted based on whole bloodto-plasma (WBP) ratios, in order to obtain whole blood biomarker concentrations. Values of biomarker concentrations (plasma or whole blood) will be reported with corresponding values of standard error of the mean (s.e.m.).

Covariate analysis

Association between clinical variables and concentration of individual blood biomarkers will be assessed. A linear regression model between biomarker concentration (as the outcome) and key clinical covariates will be generated.

Biomarker kinetics

To assess the effect of biomarker kinetics on diagnostic performance, patient population will be divided into 3-hour and 6-hour bins based on their stroke onset to blood collection time and multivariate logistic regression will be performed on each population bin separately. Alternatively, the distribution of stroke onset to blood collection times will be assessed and the population will be divided into quartiles or halves, and compared. Results from this analysis will be compared to results obtained on the whole population and will inform if the test will be limited to a specific time window from stroke onset.

Diagnostic performance

Values of diagnostic accuracy, sensitivity, specificity, positive and negative likelihood ratios will be calculated and reported with confidence intervals. ROC curve will be drawn and the area under the ROC curve will be reported with confidence intervals. Confidence intervals will be estimated via 2000 bootstrapped replicates.

Biomarker diagnostic thresholds

Thresholds of individual biomarkers already established by Pockit diagnostics will be validated for their diagnostic performance. If the accuracy achieved by the model is below acceptable levels (specificity <90% and/or sensitivity<60%) we will aim to refine the model using data from our 395 patient cohort.

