The aim of the TIME study is to validate the clinical diagnostic performance of previously defined diagnostic thresholds of Pockit diagnostics' algorithm. Results of this study will direct the development of a diagnostic test for identifying LVO patients in the field, directing them to EVT centre, ultimately enabling faster treatment, and improving patient outcomes.

3. Aim of the study

The primary aim of this study is to validate the clinical diagnostic performance of previously defined cut-off points on the plasma concentration of D-dimer and GFAP, combined with stroke severity scales (FAST-ED, FAST, EMSA, RACE, C-STAT).

The secondary aim of the study is to optimise the cut-off points of the diagnostic algorithm for LVO detection, in a larger and inter-racial patient population.

4. Study endpoints

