4.2. Secondary outcomes

Secondary outcomes will be optimised values of ut-off points for the different diagnostic algoirthms (one per stroke severity scale evaluated) obtained in a larger interracial population.

5. Study design and methodology

The TIME study is designed as an observational prospective cohort study.

This study is designed to validate candidate biomarkers according to the STARD principles (http://www.equator-network.org/reporting-guidelines/stard/).

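### The analysis meant to inform a time limit on the test refits a regression in each onset-time bin; nowhere are the pre-set cut-offs scored by onset-to-blood time (minor, cheap to improve)

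*Combined protocol and SAP*

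**What the plan says.** Section 7.4, Biomarker kinetics, states that the "patient population will be divided into 3-hour and 6-hour bins" by onset-to-blood time and that "multivariate logistic regression will be performed on each population bin separately". As an alternative, once the distribution of times has been looked at, "the population will be divided into quartiles or halves, and compared". On use, it says: "Results from this analysis will be compared to results obtained on the whole population and will inform if the test will be limited" to a given window after onset. It does not say which regression result is compared or what difference would lead to a limit.

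Elsewhere:
- Section 3 makes the primary aim the validation of "previously defined cut-off points on the plasma concentration of D-dimer and GFAP", combined with stroke scales. The thresholds paragraph of section 7.4 repeats that existing thresholds are to be validated. Neither mentions onset time.
- Section 4.2 speaks of several algorithms, "one per stroke severity scale evaluated".
- Section 7.4, Covariate analysis: "A linear regression model between biomarker concentration (as the outcome) and key clinical covariates will be generated". Onset-to-blood time is not named as a covariate.
- Section 7.4, Diagnostic performance: "Confidence intervals will be estimated via 2000 bootstrapped replicates". These intervals are not expressly tied to time groups.
- Section 7.1 lists onset-to-blood time among the data recorded for every patient, for the study of marker kinetics.

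**The concern.** Whether the test should be limited to a time window is a question about the test as it will be used, with fixed cut-offs. A regression refitted within a bin estimates that bin's own intercept and slopes. It therefore answers a different question: how well the markers could separate LVO from non-LVO in that bin if the rule were re-tuned to it.

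The two answers can differ. If D-dimer or GFAP rises or falls with time in LVO and non-LVO patients alike, refitting absorbs the shift and discrimination looks constant. A fixed cut-off does not move with the markers, so sensitivity and specificity change. A reader of the planned output could then conclude that no limit is needed without having seen the pre-set rule's performance early and late. Fine bins also hold few LVO cases, so differences between them are hard to read either way.

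**Working it through.** **1. Group sizes.** The plan gives no figures for this analysis, so I start from section 6.4: 329 evaluable patients at 20% LVO, 329 × 0.20 = 65.8, so 66 LVO and 329 − 66 = 263 non-LVO. Eligibility is under 18 hours (section 6.1), which gives 18/3 = 6 three-hour bins or 18/6 = 3 six-hour bins. Assuming an even spread of onset times (not stated in the documents):

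| Grouping | LVO per group |
|---|---|
| 3-hour bins | 66/6 = 11 |
| Quartiles | 66/4 = 16.5 |
| 6-hour bins | 66/3 = 22 |
| Halves | 66/2 = 33 |

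Over the accepted prevalence of 10–30% (33 to 99 LVO of 329), a 6-hour bin would hold 11 to 33 LVO.

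**2. Can refitted discrimination stay flat while fixed-cut-off performance moves?** The model is assumed and serves only as an illustration: three independent normal inputs with SD 1, each higher by 1.0 SD in LVO; score = their sum (SD √3 = 1.732); one cut-off set at 95% specificity overall. Markers drift linearly over 18 hours, equally in LVO and non-LVO.

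Separation on the standardised score is 3/1.732 = 1.732. Within a bin the AUC is about Φ(1.732/√2) = Φ(1.225) = 0.89, whatever the drift, because both groups move together.

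Now let two markers rise by 1.0 SD each. The sum rises by 2.0 over 18 hours, so the centres of the first and last 6-hour bins lie at 2 × (∓6/18) = ∓0.667, or ∓0.385 on the standardised scale. The drift adds variance (2²/12)/3 = 0.111, so the overall 95% cut-off is about 1.645 × √1.111 = 1.734.

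| | 0–6 h | 6–12 h | 12–18 h |
|---|---|---|---|
| Specificity | Φ(1.734 + 0.385) = 98% | Φ(1.734) = 96% | Φ(1.734 − 0.385) = 91% |
| Sensitivity | 1 − Φ(1.734 + 0.385 − 1.732) = 35% | 1 − Φ(0.002) = 50% | 1 − Φ(1.734 − 0.385 − 1.732) = 65% |

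A simulation of 400,000 patients with logistic models refitted per bin gives the same picture: refitted AUC 0.89 in all three bins, sensitivity 35/50/65%, specificity 98/96/91%.

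**3. How far this depends on the assumed drift.** Same model, LVO shifts of 0.8 to 1.2 SD:

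| Drift over 18 h | Change in sensitivity, first to last 6-hour bin |
|---|---|
| Two markers, equal and opposite | about 0 |
| One marker, 0.5 SD | 7–8 points |
| Two markers, same direction, 0.5 SD each | 13–15 points |
| Two markers, same direction, 1.0 SD each | 27–30 points |

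The documents give neither the direction of any drift nor the form in which cut-offs and scales are combined, so the whole range from about 0 to about 30 points is open.

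**4. Precision of a direct display.** Exact 95% intervals: sensitivity 15/22 (one 6-hour bin) 45–86%; 23/33 (one half) 51–84%; 7/11 (one 3-hour bin) 31–89%. Specificity 84/88 (one 6-hour bin) 89–99%.

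**The case against.** **The purpose already covers it.** The paragraph aims at diagnostic performance and compares with whole-population results, which include sensitivity and specificity. For quartiles or halves it says only that they are compared, with no regression named. That wording leaves room for scoring the pre-set cut-offs, but it does not say so. Refitting also suits the secondary aim of optimising cut-offs, which is a reason to keep it as exploratory work.

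**Drift would show elsewhere.** This largely stands as regards detection. Under the illustrative model with 329 patients, regressing each marker on time at 5% picks up a 0.5 SD drift in at least one of the two markers in about 85–90% of trials, and a 1.0 SD drift in nearly all. The refitted intercept would also move. But onset time is not named as a covariate, the plan does not say intercepts are compared, and neither result gives the effect on sensitivity or specificity.

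**Stronger readings that the documents do not support.**
- A reader might infer that an important drift will be missed. The size of any drift is unknown, and its effect on the rule may be nil.
- A reader might infer that chance differences between bins will often be taken for a time window. Any such rate needs an AUC margin and a best-bin rule, and the plan states neither.
- A reader might count four groupings as open. The 3-hour and 6-hour bins are both planned; the open choice is between those and quartiles or halves.
- A reader might want a formal test to decide the window. A permutation test of positivity on time with a quadratic term, at 2.5% each in LVO and non-LVO, finds the 0.5 SD drift in only about 20% of trials and the 1.0 SD drift in about 60%. That is worse than the simple marker regression, so it should not be the gate.

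**Conclusion.** The concern holds as a minor point. The method named for informing a time limit does not examine the rule being validated, and no section says that rule will be scored by onset-to-blood time. Flat refitted AUC can coexist with changing performance at fixed cut-offs. The possible size, about 0 to about 30 points of sensitivity across 6-hour bins, is an illustration that rests on a sum score, normal inputs and drifts of 0.5 to 1.0 SD. It is not a forecast for this trial. The small-group counts rest on 66 LVO spread evenly over 18 hours. This is a supporting analysis that informs a decision rather than making it, and the primary estimates are untouched.

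**What to change.** In section 7.4, Biomarker kinetics:
1. State that the pre-set algorithm will be applied unchanged, and that its sensitivity and specificity will be reported with exact 95% intervals in one onset-to-blood-time grouping fixed before database lock (for example 6-hour bins or halves), beside the whole-cohort values.
2. Name onset-to-blood time as a covariate in the planned marker regression.
3. Label the bin-specific refitted regressions exploratory.
4. Rest any statement about a time window on items 1 and 2 together, label it descriptive, and say that the absence of a visible difference does not show constant performance.

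No gatekeeping test, alpha split or curvature terms are needed. The cost is a few sentences and one extra table, since onset-to-blood time is already recorded (section 7.1). The drawback is that the intervals within groups will be wide, so the table can reveal a gross change but cannot rule out a moderate one.

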6.1. Inclusion criteria

- 1) Older than 18 years at time of consent;
- 2) Evaluated in the emergency department with suspected and code stroke activated.
- 3) Time from stroke onset < 18 hours

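### The time-window decision rests on comparing each onset-time bin with a whole population that contains it, which understates time differences in sensitivity, specificity and accuracy at fixed cut-offs.

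*Combined protocol and SAP*

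**What the plan says.** The Biomarker kinetics paragraph of section 7.4 asks whether time since onset affects diagnostic performance. Patients are "divided into 3-hour and 6-hour bins based on their stroke onset to blood collection time". The model is then fitted bin by bin: "multivariate logistic regression will be performed on each population bin separately". As an alternative, "the population will be divided into quartiles or halves, and compared". The closing sentence applies to either option: "Results from this analysis will be compared to results obtained on the whole population and will inform if the test will be limited". The limit in question is a window of time since onset.

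Section 6.1 sets the onset window ("Time from stroke onset < 18 hours"), so there are up to six 3-hour bins or three 6-hour bins. The only interval method in section 7.4 is in the Diagnostic performance paragraph: "Confidence intervals will be estimated via 2000 bootstrapped replicates". It is not tied to a difference between a bin and the whole. The kinetics paragraph gives no between-group test for the 3-hour and 6-hour bins, no time interaction, no interval for a difference, no treatment of the overlap and no decision margin.

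**The concern.** The whole-population result is a weighted mixture of the bin and the remaining patients, so setting a bin beside it compares the bin partly with itself. The larger the bin, the more of a real difference disappears from view. The two figures are also positively correlated, so ordinary two-sample reasoning gives the wrong error rate.

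This matters because it is the only comparison the plan expressly links to the time limit. Sensitivity, specificity and accuracy at previously defined cut-offs are among the primary outcomes (sections 3 and 4.1), and they are the measures for which the dilution is exact. A fall in one of them early or late after onset could look smaller than it is and be passed over when the usable window is set.

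**Working it through.** **Inputs from the protocol.** Section 6.4 gives 329 evaluable patients at 20% prevalence: 329 × 0.20 = 65.8, i.e. the stated 66 LVO, leaving 329 − 66 = 263 non-LVO. The kinetics analysis has no sample size, effect size or power of its own to reproduce.

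**Assumptions.** Equal-sized bins unless stated otherwise. The effect sizes below are illustrative and do not come from the protocol.

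**Step 1: dilution.** Let f be the bin's share of the relevant patients (LVO for sensitivity, non-LVO for specificity, all for accuracy). With the same decision rule applied to everyone:

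whole = f × bin + (1 − f) × rest, so bin − whole = (1 − f) × (bin − rest).

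The factor 1 − f is 0.50 for halves, 0.67 for 6-hour bins, 0.75 for quartiles and 0.83 for 3-hour bins. A bin holding 60% of patients would show 0.40 of the gap.

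**Step 2: specificity example.** Take 85% in one bin, 95% elsewhere and 263 non-LVO. For halves (131.5 each):
- Bin v rest: variances 0.85 × 0.15 / 131.5 = 0.000970 and 0.95 × 0.05 / 131.5 = 0.000361; SE = √0.001331 = 0.0365; z = 0.10 / 0.0365 = 2.74.
- Bin v whole, overlap handled: difference 0.05, SE = 0.5 × 0.0365 = 0.0182; z = 2.74, unchanged.
- Bin v whole, read as independent: variance of the whole = 0.25 × 0.000970 + 0.25 × 0.000361 = 0.000333; SE = √(0.000970 + 0.000333) = 0.0361; z = 0.05 / 0.0361 = 1.39.

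Power is Φ(z − 1.96) when the overlap is handled. When it is ignored, power is Φ((difference − 1.96 × SE assuming independence) / correct SE). With equal variances, the true two-sided error rate of the independent reading is 2[1 − Φ(1.96 × √((1 + f)/(1 − f)))].

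| Grouping | Gap shown (true 10 points) | z, overlap handled | z, read as independent | Power, handled | Power, independent | True error rate, nominal 5% |
|---|---|---|---|---|---|---|
| Halves | 5.0 | 2.74 | 1.39 | 78% | 13% | 0.07% |
| 6-hour | 6.7 | 2.41 | 1.60 | 67% | 29% | 0.6% |
| Quartiles | 7.5 | 2.14 | 1.60 | 57% | 32% | 1.1% |
| 3-hour | 8.3 | 1.79 | 1.49 | 43% | 29% | 2.0% |

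**Step 3: sensitivity example, by simulation.** Assume 66 LVO, sensitivity 80% in one group and 50% in the other, and a pooled two-proportion z test at two-sided 5%.
- Split 33/33: whole = 65%. The true gap is 30 points and each half differs from the whole by 15. Power is 75% for half v half, but 25% (better half) or 17% (poorer half) against the whole read as independent.
- Split 50/16, with 80% in the larger group: whole = (50 × 0.80 + 16 × 0.50) / 66 = 72.7%. The larger group differs from the whole by 7.3 points and the smaller by 22.7. Power is about 65% for group v rest. Against the whole read as independent it is about 1% for the larger group and 40% for the smaller.
- No true difference, halves at 65%: about 0.1% rejections against a nominal 5%.

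**Step 4: where the identity does not apply.** It needs one rule applied to both bin and whole. AUC is not a weighted average: if marker levels shift by 2 SD between two equal bins, each with AUC 0.921, the pooled AUC is 0.835. Both bins then differ from the whole by 0.086 although they do not differ from each other. Refitting per bin also pushes the other way. With no time effect, three assumed predictors and AUC about 0.85, the apparent AUC in a refitted bin exceeded the whole-population value on average by 0.003 (halves), 0.007 (6-hour), 0.012 (quartiles) and 0.017 (3-hour).

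**The case against.** A reader might infer that every real time effect is shrunk and that the plan therefore leans towards finding no difference. The documents do not support this, for four reasons.

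- **Refitting.** The plan fits a separate regression in each bin and does not say that the fixed cut-offs are scored there. The dilution identity does not cover refitted models or AUC, and those can exaggerate a gap. This stands, and it limits the point to fixed-cut-off measures.
- **No test is named.** The power losses arise only if overlapping results are treated as independent. The plan does not prescribe that, and a bootstrap of the bin-minus-whole difference, resampling both together, would leave z unchanged. This stands for power. It does not restore the size of the displayed effect, which a time-window decision has to weigh, and the plan does not specify such a bootstrap.
- **A group comparison may already exist.** The wording for quartiles or halves can fairly be read as group against group. That covers only the alternative option; the 3-hour and 6-hour bins have no counterpart.
- **The loss is visible anyway.** Each bin's own result will be produced, and a poor small bin stands out (22.7 points in the 50/16 example). Section 7.4 also names specificity below 90% or sensitivity below 60% as unacceptable for the model, though not expressly for bins. With 3-hour bins most of the gap survives. This tempers the consequence: the 1% power figure belongs to the larger, better group only and should not be quoted alone.

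Bin against whole also answers a legitimate question: how a time-restricted test would compare with an unrestricted one. It does not answer whether performance changes with time, which is the paragraph's stated purpose.

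**Conclusion.** The point holds within limits. The plan ties the time-window decision to a part-whole comparison. For sensitivity, specificity and accuracy at fixed cut-offs, the visible gap is then 50% to 83% of the bin-versus-rest gap across the groupings named, if bins are equal, and less for a dominant bin. Reading the overlapping figures as independent would also make the comparison far too conservative, but that is a risk left open by silence, not a stated method. For AUC and refitted models the comparison is unreliable in either direction, so no general bias towards no difference can be claimed. The shrink factors follow from arithmetic and the bin shares; the power figures depend on the assumed effect sizes and splits. Because a stated comparison can be replaced by a clearly better one, this should be changed and goes beyond a request for detail.

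**What to change.** Replace the closing sentence of the Biomarker kinetics paragraph with wording such as: *The pre-defined cut-offs will be scored in each onset-time group. Each group will be compared with the patients outside it, or all groups will be assessed through a time-by-test interaction in one model of all patients, with a 95% bootstrap confidence interval for the difference. The whole-population result will be shown for reference only. The time-window decision will rest on this difference together with each group's own performance.* The sponsor should also say whether quartiles or halves are compared with each other.

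The cost is analysis-plan wording only, with no extra patients or data. The change does not cure sparse bins. With equal 3-hour bins there are about 66 / 6 = 11 LVO and 263 / 6 ≈ 44 non-LVO per bin. Bin against rest then has about 43% power for specificity 85% v 95% and about 25% for sensitivity 60% v 80%. Intervals will be wide, and an inconclusive one should not be read as evidence that time has no effect.

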The TIME study is a multi-centre, observational prospective cohort study. Patients referred to the emergency department or stroke unit with a suspected stroke will be enrolled in the study. Up to 400 patients will be recruited and requested to provide one venous blood sample. Blood samples will be processed on site and frozen. Samples will be analysed retrospectively via standard laboratory assays.

Outcomes

The main outcome of the TIME study will be the validation of the clinical diagnostic performance of Pockit diagnostics' algorithm for LVO detection. This study will validate previously defined diagnostic thresholds for LVO identification.

2. Rationale

Stroke is among the leading causes of death and disability worldwide. Ischaemic stroke caused by large vessel occlusion (LVO) contributes disproportionally to these figures and accounts for 62% of post-stroke disabilities and 96% of post-stroke mortality¹.

Acute ischaemic stroke patients with LVO can be effectively treated with endovascular thrombectomy (EVT)², but this treatment is only available in comprehensive stroke centers (CSC) or other EVT-capable centers. Inter-hospital transfer of LVO patients from primary stroke centers to EVT-capable centers significantly delays time to treatment and leads to higher disability rates³. Identification of LVO patients in the pre-hospital setting (e.g. within an ambulance) could enable the transfer of LVO patients to EVT-capable centers directly, reducing time to treatment, functional disabilities, and deaths.

Multiple studies have investigated the ability of brief pre-hospital stroke assessment scales to identify LVO strokes in the field. Despite this, these severity scales lack the sensitivity and specificity required for triaging LVO patients with confidence, resulting in false negatives in patients with LVO and milder stroke as well as false positives in patients with stroke mimics or haemorrhagic strokes^{4,5}. A more accurate diagnostic test able to complement these assessment scores and direct LVO patients to EVT-capable centers is much needed.

Pockit diagnostics have ventured a novel strategy for the identification of LVO. By combining the measurement of D-dimer and GFAP with pre-hospital stroke severity scales (e.g. FAST-ED⁶), Pockit diagnostics have created a powerful diagnostic algorithm that has demonstrated accuracy of 95% (95%CI 87-99%) and specificity of 98% (95% CI 92-100%) for LVO detection⁷.

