4.1. Primary outcomes

Primary outcomes of the TIME study will be values of diagnostic accuracy, sensitivity, specificity, positive likelihood ratio (LR+) and negative likelihood ratio (LR-) of the model composed of D-dimer, GFAP and stroke severity scales (FAST-ED, FAST, EMSA, RACE, C-STAT) for identification of LVO.

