6.4. Sample size estimation

The proposed intended use of the test is to rule in patients with LVO to redirect them to EVT-capable centers from a population of suspected stroke, thus we powered the study on specificity. Assuming a prevalence of 20%, a minimum specificity of 90%, a two-tailed 5% type I error rate (**a**) and 90% power (**β**), a sample size of 329 suspected stroke patients with 66 LVO cases would detect a diagnostic specificity of 95% (95%CI: 90%–100%) for each

algorithm. Accounting for 20% of data loss due to missing patient data or sample lysis, a final number of 395 patients will be required.

Sample size estimation was performed according to Chu and Cole⁸.

Prevalence of LVO/ischemic stroke will be monitored during recruitment to ensure that calculated sample size is appropriate for actual prevalence. A prevalence in the range of 10-30% LVO will be accepted. In case observed prevalence will be outside the acceptable range, sample size will be re-estimated and recruitment size adjusted accordingly.

7. Data management

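### Section 6.4's 329 patients fit a one-sided 5% test of specificity, not the stated two-tailed 5%, and section 7.4 never ties validation to that test

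*Combined protocol and SAP*

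**What the plan says.** The abstract states the purpose: "This study will validate previously defined diagnostic thresholds for LVO identification". Section 4.1 defines the primary outcomes as estimates: "Primary outcomes of the TIME study will be values of diagnostic accuracy, sensitivity, specificity" and the two likelihood ratios.

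Section 6.4 sets the study up as a test of specificity: "Assuming a prevalence of 20%, a minimum specificity of 90%, a two-tailed 5% type I error rate", with 90% power. It concludes that 329 patients, 66 of them with LVO, "would detect a diagnostic specificity of 95% (95%CI: 90%–100%) for each" algorithm, and it cites an exact method. It also allows the case mix to vary: "A prevalence in the range of 10-30% LVO will be accepted".

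Section 7.4 attaches one interval method to the performance measures: "Confidence intervals will be estimated via 2000 bootstrapped replicates". It gives no confidence level, no bootstrap type and no decision that the interval serves. Its one numerical bar is "If the accuracy achieved by the model is below acceptable levels (specificity <90% and/or sensitivity<60%) we will aim to refine the model".

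Section 3 adds that "The secondary aim of the study is to optimise the cut-off points of the diagnostic algorithm for LVO detection". Section 4.2 makes the optimised cut-offs the secondary outcome.

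**The concern.** Three things do not join up.

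1. The sample size, the error rate and the power in section 6.4 should agree under the method cited there.
2. A study sized as a test against a 90% minimum should say in its analysis section when that test is passed. Section 7.4 does not refer back to it. The 90%/60% sentence could be taken for the pass mark by default, and nothing in it mentions an interval.
3. Cut-offs are to be re-chosen on the same patients, with no hold-out set or optimism correction described.

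At stake is the meaning of the word validated. An algorithm whose true specificity lies below the study's own minimum could be given that label, and a reader could not tell which error rate stands behind it. Section 3 follows a statement that the results will direct development of the test, so the label has consequences.

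**Working it through.** **Inputs (section 6.4).** Minimum specificity p0 = 0.90; target p1 = 0.95; 329 patients, 66 with LVO, so 329 − 66 = 263 without LVO; 90% power; two-tailed 5%, which is 2.5% in the upper tail.

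**Reproducing 329.** Let X be the number of correct negatives among n non-LVO patients, X ~ Binomial(n, p). Take r as the smallest count with P(X ≥ r | 0.90) ≤ α. Power is P(X ≥ r | 0.95).

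- One-sided α = 5%: power stays at or above 90% from n = 263, and 263/0.8 = 328.75, which rounds up to 329. This matches the plan.
- Upper tail 2.5%: power first reaches 90% at n = 292 and stays there from n = 316. These give 292/0.8 = 365 and 316/0.8 = 395 analysable patients. Neither matches.

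**What 263 non-LVO patients give.**

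| Rule | Pass mark | Actual upper-tail error at 90% | Power at 95% |
|---|---|---|---|
| One-sided 5% | 245/263 (93.2%) | 4.9% | 92.9% |
| Two-tailed 5% | 247/263 (93.9%) | 1.7% | 83.0% |

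**Over the accepted prevalence range, with 329 analysable.**

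| LVO prevalence | Non-LVO | One-sided power | Two-tailed power |
|---|---|---|---|
| 10% | 296 | 93.0% | 89.2% |
| 20% | 263 | 92.9% | 83.0% |
| 30% | 230 | 88.4% | 73.7% |

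**The 90% trigger read on observed values.** 236/263 = 89.7% and 237/263 = 90.1%, so 237 is the first count that clears the specificity part. Its exact 95% interval is 85.9% to 93.4%.

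| True specificity | P(X ≥ 237) | P(X ≥ 247) |
|---|---|---|
| 90% | 52.7% | 1.7% |
| 89% | 32.3% | 0.4% |
| 88% | 16.9% | 0.1% |

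These concern specificity alone. Clearing the whole 90%/60% bar also needs sensitivity of at least 60%.

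**Bootstrap against exact, 263 non-LVO.** A 2000-replicate percentile bootstrap (the percentile type is an assumption, since section 7.4 names none) was simulated 2000 times at each count.

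- At 247, the exact two-sided 95% lower limit is 90.3%, and the bootstrap limit is above 90% in every run. The two agree.
- At 246, the exact limit is 89.9%, but the bootstrap limit is about 90.4% and above 90% in every run. This count has probability 5.8% at a true 95%.
- At 245, the exact limit is 89.4%. The bootstrap limit is above 90% in 68% of runs when only non-LVO patients are resampled, and in 29% when all 329 are. This count has probability 4.2% at a true 95%. Only here does the answer depend on scheme and seed.

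**Re-chosen cut-offs.** The documents do not fix the size of the optimism. As an illustration only, assume two independent normal markers separated by 1.0 to 1.5 SD, a both-positive rule, cut-offs maximising the Youden index, and 66 against 263 patients. Over 200 simulations, apparent sensitivity was 5.6 to 6.5 points too high and specificity 1.2 to 1.9 points too high.

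**The case against.** The strongest reply is that this is an estimation study. The primary outcomes are values with intervals, reported along STARD lines, and such a study needs no binary verdict. At 237/263 a reader would see an interval of roughly 86% to 93% and judge accordingly. That stands as far as it goes: the harm needs someone to use the word validated despite the interval. It does not explain why section 6.4 poses a test that the analysis then leaves out.

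Several stronger readings are tempting, and the documents do not support them.

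- *That 329 is an arithmetic error.* It is the exact one-sided 5% figure, so the fault is a mismatch with the two-tailed label. The only two-sided calculation found near it is a Wald limit (n = 261, 261/0.8 = 326.25, so 327). That is not an exact method, and at n = 263 its upper-tail error is 4.9%.
- *That the study is underpowered whatever the truth.* At the 98% specificity reported in the rationale, power exceeds 99.9% under either rule. The shortfall applies at the design value of 95%.
- *That recruiting 395 already covers the two-tailed requirement.* The plan's 395 is 329 × 1.2 = 394.8, before losses. The two-tailed 395 counts analysable patients.
- *That the plan names no interval.* It names the bootstrap. The level, the type and any decision use are missing.
- *That the plan defines validation as clearing 90%/60% on observed values.* No section says so; the sentence only triggers refinement.
- *That optimism contaminates the validation.* Estimates at the pre-set cut-offs are unaffected. Section 4.2 lists the cut-off values themselves as the outcome, and the plan does not expressly say that performance at them will be reported.

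**Conclusion.** The point holds, and the plan should be changed. As written, the power in section 6.4 is wrong for its stated error rate: 83.0% instead of 90% with 263 non-LVO patients, and between 89.2% and 73.7% across the accepted prevalence range. This rests on the exact binomial method that section 6.4 cites and on all 329 patients being analysable.

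Section 7.4 leaves validation without a criterion. The consequence of using the refinement trigger in its place is conditional: if it is read on observed values and treated as the pass mark, a true specificity of 89% clears it 32.3% of the time and 88% clears it 16.9% of the time. The difference between bootstrap and exact limits is smaller. It affects counts of 245 and 246, with probabilities of 4.2% and 5.8% at a true 95%.

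The optimism point is secondary. It applies only if sensitivity or specificity is reported at re-chosen cut-offs, and its size cannot be derived from the documents.

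**What to change.** 1. **Section 6.4.** Either keep two-tailed 5% and restate the power as about 83% for 263 non-LVO patients, or state one-sided 5% and keep 329.
2. **Section 7.4, decision rule.** Add: *Specificity of an algorithm at the pre-set cut-offs is called validated only if its exact (Clopper-Pearson) lower limit, on the actual number of non-LVO patients, exceeds 90%.* Name the limit in the same sentence: that of the two-sided 95% interval if two-tailed 5% is kept, or the one-sided 95% lower limit if one-sided 5% is stated.
3. **Section 7.4, intervals.** Use exact intervals for sensitivity and specificity. Keep the 2000 bootstrap replicates for accuracy, likelihood ratios and the area under the ROC curve. Keep the 90%/60% sentence only as the refinement trigger.
4. **Re-chosen cut-offs.** Label any performance reported at them as development. Report it with a bootstrap optimism correction that repeats the cut-off search in each replicate, under a criterion fixed in advance.

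**Cost.** Wording and modest programming. Neither option in item 1 needs more patients at 20% prevalence, though at 30% even one-sided power is 88.4%. Keeping both two-tailed 5% and 90% power would need 365 to 395 analysable patients. Allowing for 20% loss, that means recruiting between 438 (365 × 1.2) and 494 (395/0.8), above the ceiling of 400. With 263 non-LVO patients, an algorithm with true specificity 95% would miss the bar 17% of the time two-tailed or 7% one-sided. Corrected figures at refined cut-offs will look less favourable.
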